#### 5.1.3.6 Conclusion

Based on the 3+3 design, 100 mg PO daily was determined to be the MTD with 1 out of 6 evaluable patients experiencing a DLT, while 150 mg PO daily resulted in 2 out of 3 evaluable patients with a DLT. The side effect profile at 100 mg PO daily was considered acceptable and consistent with the expected side effect profile of the cisplatin chemoradiation therapy backbone. Exposures were comparable to previous reports (Chao 2012), patients treated at 150 mg did not achieve higher plasma exposures than at 100 mg PO, and patients with DLT did not appear to have markedly different exposures than patients that without DLT.

In summary, 100 mg triapine PO daily in combination with cisplatin based chemoradiation is the appropriate dose to take forward into the expansion phase of this phase 1 trial.

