13.1.1 The RP2D will be determined as described in section 5.1.2. Once the RP2D is determined, two expansion cohorts will be enrolled. Subjects will be enrolled into a non-HIV+ cohort (n=12) to further expand pharmacokinetic investigations and provide additional safety information. Additionally, up to 28 HIV+ cervical cancer patients (including the patients who were treated at the RP2D during the dose escalation stage) will be treated on RP2D to determine whether active HIV antiretroviral therapy impacts the antitumor activity of triapine. A Bayesian continuous monitoring will be used to ensure that the true DLT rate is controlled at 20%. To establish the stopping rule, a week prior distribution of DLT rate is set to be beta ( $\alpha=1, \beta=5$ ). If the posterior probability that the true underlying DLT rate exceeds 20% at RP2D is 70% or higher then the study accrual will be suspended and the toxicity data will be examined by the PI and the research team, who will subsequently decide on whether the trial should be terminated or not.

The enrollment suspension rule using the Bayesian analysis mentioned above can be represented as a table of possible outcomes for DLTs, as shown below.

Bayesian rule for suspending enrollment	
Suspend accrual if n patients experience a DLT	in N patients treated
2	3-4
3	5-8
4	9-13
5	14-17
6	18-22
7	23-26
8	27

The operating characteristics of this study design can be expressed in terms of probability of early suspending the enrollment at RD2P under the assumptions of various the true rates of DLT. The following table calculated these probabilities for a single dose level based on the simulation of 10,000 hypothetical trials.

Frequentist properties of Bayesian rule for suspending enrollment		
Probability of DLT	Probability of suspending	Median sample size for

	the enrollment	each dose level
0.1	0.10	28
0.17	0.32	28
0.2	0.45	28
0.25	0.66	13
0.3	0.83	8

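### The suspension table in section 13.1.1 omits two outcomes that its own Bayesian rule triggers: 2 DLTs in 2 patients and 8 DLTs in 28

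*Combined protocol and SAP*

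**What the plan says.** Section 13.1.1 specifies continuous Bayesian monitoring of the DLT rate at the RP2D. The "prior distribution of DLT rate is set to be beta" with parameters 1 and 5. Accrual is suspended if the "posterior probability that the true underlying DLT rate exceeds 20% at RP2D is 70% or higher then the study accrual will be suspended", after which the investigator and research team review the toxicity data. No minimum number of patients is given before the rule applies, either here or in section 13.2.1.

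The section continues: "The enrollment suspension rule using the Bayesian analysis mentioned above can be represented as a table of possible outcomes for DLTs". The columns are "Suspend accrual if n patients experience a DLT" and the number treated. The rows are 2 in 3-4, 3 in 5-8, 4 in 9-13, 5 in 14-17, 6 in 18-22, 7 in 23-26 and 8 in 27.

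Operating characteristics follow, "based on the simulation of 10,000 hypothetical trials". The probability of suspension is 0.10, 0.32, 0.45, 0.66 and 0.83 at true DLT rates of 0.10, 0.17, 0.20, 0.25 and 0.30. The median sample size is 28, 28, 28, 13 and 8.

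On who is counted, the section refers to "up to 28 HIV+ cervical cancer patients (including the patients who were treated at the RP2D during the dose escalation stage"; the inclusion of escalation patients is mentioned only for that cohort. Section 5.1.3.6 reports the data already in hand at the expansion dose: "100 mg PO daily was determined to be the MTD with 1 out of 6 evaluable patients experiencing a DLT".

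**The concern.** A lookup table for a safety rule exists so that nobody has to compute a posterior at each review. It should therefore contain every outcome at which the rule fires. This one begins at N = 3, although under continuous monitoring with no run-in the rule can fire at N = 2. The missing outcome, 2/2, has a higher posterior than either outcome listed in the first row (2/3 and 2/4). The table also stops one patient short of the 28 on which the operating characteristics are based. Someone relying on the table alone would find no instruction to suspend at 2/2 or at 8/28, while the sentence above it requires suspension at both.

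**Working it through.** **Inputs (all from section 13.1.1 unless noted).** Prior Beta(1,5); DLT threshold 0.20; posterior trigger 0.70; no minimum N; maximum N of 28; 1 DLT in 6 evaluable patients at 100 mg (section 5.1.3.6).

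**Formula.** With x DLTs in N patients the posterior is Beta(1 + x, 5 + N - x). Because the parameters are integers, P(rate > 0.2) = P(Binomial(5 + N, 0.2) ≤ x). The boundary is the smallest x for which this is at least 0.70.

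**Printed rows first.** For every N from 3 to 27 the calculated boundary equals the printed one. The prior, threshold and trigger are therefore being read as intended.

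**Lower end.** For 2/2: P(Binomial(7, 0.2) ≤ 2) = 0.8^7 + 7(0.2)(0.8^6) + 21(0.04)(0.8^5) = 0.2097 + 0.3670 + 0.2753 = 0.852.

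| DLTs/N | Posterior | Rule | Table |
|---|---|---|---|
| 1/1 | 0.655 | continue | no entry |
| 2/2 | 0.852 | suspend | no entry |
| 2/3 | 0.797 | suspend | suspend |
| 2/4 | 0.738 | suspend | suspend |
| 2/5 | 0.678 | continue | continue |

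**Upper end.** 7/27 gives 0.698 (continue) and 8/27 gives 0.825 (suspend, printed). 7/28 gives 0.666 (continue) and 8/28 gives 0.800 (suspend, no entry). Without an earlier suspension, 8/28 is reached only from 7/27 with a DLT in patient 28.

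**Operating characteristics.** These were computed exactly: the distribution of the DLT count is carried forward patient by patient to N = 28, and paths that reach the boundary are removed.

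| True rate | Printed | Table as printed, from zero | With N = 2 added | With N = 2 and N = 28 added | Table as printed, from 1/6 |
|---|---|---|---|---|---|
| 0.10 | 0.10 | 0.093 | 0.093 | 0.093 | 0.048 |
| 0.17 | 0.32 | 0.322 | 0.322 | 0.324 | 0.210 |
| 0.20 | 0.45 | 0.450 | 0.450 | 0.453 | 0.314 |
| 0.25 | 0.66 | 0.658 | 0.658 | 0.662 | 0.505 |
| 0.30 | 0.83 | 0.819 | 0.819 | 0.824 | 0.684 |

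Counting from zero agrees with the printed probabilities to within about one percentage point and gives the printed medians exactly. Counting from 1/6 does not: at a 20% rate it gives 0.31 against 0.45, and the last two medians become 26 and 19 instead of 13 and 8. The printed design is therefore a count from zero.

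**Size of the N = 2 gap.** The probability of a 2/2 start is p squared: 0.2² = 0.04 at a true rate of 20% and 0.3² = 0.09 at 30%. Once a third patient is treated, 2 in 3 is met whatever that patient's outcome. The N = 2 row therefore leaves every suspension probability unchanged and only brings the suspension forward by one patient.

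**The case against.** A reader might infer that the plan permits a third patient to be treated after the rule has said stop. The documents do not support that. The operative instruction is the sentence with the 70% trigger, and the table is offered as a representation of it. A missing row is not permission to continue, and at 2/2 the sentence already requires suspension. Nor do the documents say that sites or the slot-reservation system apply the table. Section 13.2.1 gives weekly DLT review to the investigator and the phase I clinical team. The table would have to be used alone, against the text, for the gap to matter.

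N = 2 may also be out of reach. The rule concerns the DLT rate at the RP2D, and six evaluable patients have been treated at that dose with one DLT. If they count, monitoring starts at 1/6 (posterior 0.32), and two immediate DLTs give 3/8 (0.75), which the printed 5-8 row catches. This stands as a possibility. The text does not settle who counts, and the printed operating characteristics fit only a count from zero.

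Finally, p squared is an upper bound. Expansion accrual is continuous, at about one patient per 5 weeks, with a DLT window of about 5 weeks that delays can lengthen. Patient 3 may already be on treatment when the second DLT is known, and an added row would not change that.

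An intended run-in of three patients would explain the first row, but the plan states none. The mismatch between text and table therefore remains.

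**Conclusion.** The table does not fully represent its rule: it omits N = 2 (2/2, posterior 0.85) and N = 28 (8/28, posterior 0.80). This is a minor defect of completeness, not a flaw in the rule.

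- **At N = 2:** at most about one extra patient, with probability at most 4% at a true DLT rate of 20% and 9% at 30%. This assumes a count from zero, use of the table without the text, and a second DLT known before patient 3 starts. Suspension probabilities do not change. There is no effect if the six patients already treated at 100 mg count.
- **At N = 28:** the added row raises the calculated probability of suspension by at most about half a percentage point (0.819 to 0.824 at a true rate of 30%). By then a 28-patient count is full, so the row matters only if other accrual at the RP2D is still open.

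The posteriors rest only on the stated prior, threshold and trigger. The unresolved question of which patients make up N decides whether the lower gap can be reached at all.

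**What to change.** In the suspension table, change the first row from 3-4 to 2-4 and the last row from 27 to 27-28, so that the table matches the stated posterior rule. In the same edit, state which patients count towards N: whether the six evaluable patients already treated at 100 mg are included, and whether the two expansion cohorts are pooled. If they are pooled, N could reach 12 + 28 = 40 and the table would need further rows.

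The cost is two table cells and one sentence. The two cells need no new simulation: the N = 2 row leaves the printed operating characteristics as they are, and the N = 28 row moves them by no more than about half a percentage point. They would have to be recalculated only if the sponsor decides that the count does not start at zero or runs beyond 28.

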### 13.2 Sample Size/Accrual Rate

13.2.1 The number patients accrued to the study will depend on the MTD; an additional 12 cervical cancer patients may be treated at the RP2D to further define the spectrum of toxicities associated with the regimen and up to an additional 28 HIV+ patients will be enrolled to explore whether active (HIV) antiretroviral therapy impacts the antitumor activity of triapine. Although unlikely to happen, for the worst-case scenario, we could have needed  $6 \times 6 = 36$  patients for the phase dose escalation portion of the protocol, 12 for the non-HIV+ expansion cohort and none of the 6 patients on the MTD (or RP2D) is HIV+ cervical cancer patient. Thus, the maximum number of patients for this trial is  $36 + 12 + 28 = 76$ . Patients who do not complete at least 80% the first cycle of therapy and do not suffer a DLT which leads to the termination of the treatment during the observation period (5 weeks excluding treatment delay period) will not be evaluable and will be replaced. Review of patient toxicity and DLT monitoring will be conducted on a weekly basis by the PI and Phase I clinical team.

We expect that the accrual rate will be approximately 1 per 5 weeks. The follow-up period of the primary endpoint, DLT, is approximately 5 weeks after the starting of the treatment (excluding the treatment delay time as described in section 5.5). During the 3+3 dose escalation stage, we will allow the first 2 patients to be enrolled without stopping. During the expansion cohort, the patients will be accrued continuously. On the other hand, the treatment may be delayed during the DLT follow up period as described in section 5.5. Therefore, for a portion of the patients, the overall follow up time may be longer than 5 weeks. Thus, the accrual rate of 1 per 5 weeks is an estimate considering the facts stated above.

### PLANNED ENROLLMENT REPORT

Racial Categories	Ethnic Categories		Total	
	Not Hispanic or Latino	Hispanic or Latino		
American Indian/ Alaska Native	0	0	0	
Ethnic Categories				

Asian	1	0	1
Native Hawaiian or Other Pacific Islander	0	0	0
Black or African American	3	0	3
White	72	0	72
More Than One Race	0	0	0
Total	76	0	76

PHS 398 / PHS 2590 (Rev. 08/12 Approved Through 8/31/2015)

OMB No. 0925-0001/0002

### 13.3 Data Analysis

#### 13.3.1 Analysis Sets

Evaluable patients: patients who meet all of the protocol inclusion/exclusion criteria and begin treatment with the protocol regimen.

Evaluable patients for DLT: evaluable patients who received at least 80% of the treatment intended during the DLT follow up period as defined in section 5.5 and patients who received any amount of treatment and experienced a protocol defined DLT which leads to the termination of the treatment are evaluable for DLT.

Safety set: data from all evaluable patients who receive initial treatment of the study treatment will be used in the analysis of safety.

Efficacy set: data from all evaluable patients who receive initial treatment of the study treatment will be used in the analysis of efficacy endpoints.

PK and correlative biomarker set: the data from all study-eligible patients (i.e. those meeting all of the protocol inclusion/exclusion criteria) who begin the study treatment and have adequate blood and tissue samples taken will be used in the analyses to address the PK and correlative biomarker aims.

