### 5.5 Definition of Dose-Limiting Toxicity

DLTs are defined as the following adverse events if considered at least “possibly related” to a component of the study therapy and which occur from the start of treatment until completion of EBRT, prior to initiation of brachytherapy (i.e. the first 5 weeks if no treatments are missed):

- Any nausea, vomiting, diarrhea and elevation of serum creatinine level Grade 3 toxicity **not resolved with maximal intervention to Grade 0-2 over 7 days (except alopecia and fatigue);**
- Any nausea, vomiting, diarrhea and elevation of serum creatinine level Grade 4 toxicity
- Any other non-hematologic toxicity  $\geq$ Grade 3;
- Any hematologic toxicity of  $\geq$  Grade 4;
- Grade  $\geq$ 3 dyspnea;
- Inability to deliver at least 20 of the scheduled 25 administrations of triapine at the planned dose, **allowing for 2 weeks to make up missed radiation days.**
- Inability to deliver at least 4 of the scheduled 5 administrations of IV cisplatin at the planned dose.

Dose escalation will proceed within each cohort according to the following schema, unless stated otherwise.

Number of Patients with DLT at a Given Dose Level	Escalation Decision Rule
0 out of 3	Enroll 3 patients at the next dose level.
$\geq$ 2	Dose escalation will be stopped. This dose level will be declared the maximally administered dose (highest dose administered). Three additional patients will be enrolled at the next lowest dose level if only 3 patients were treated previously at that dose.
1 out of 3	Enter at least 3 more patients at this dose level. 
 
• If 0 of these 3 patients experience DLT, proceed to the next dose level.
 
• If 1 or more of this group suffer DLT, then dose escalation is stopped, and this dose is declared the maximally administered dose. Three (3) additional patients will be enrolled at the next lowest dose level if only 3 patients were treated previously at that dose.
 

≤1 out of 6 at highest dose level below the maximally administered dose
	
This is generally the Recommended Phase 2 Dose (RP2D). At least 6 patients must be enrolled at the RP2D (section 5.1.2).

--	---

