## 6.6 Methemoglobinemia

If patients had prolonged methemoglobinemia or hypoxia requiring dose adjustment during any of the observation periods noted in the table above (5.3.3.1 Clinical Monitoring for Methemoglobin), follow the schema until stable.

Please note, it is the *trend* in the O2 saturation that is of importance. Since pulse oximetry is known to be unreliable in the presence of significant methemoglobinemia, weight should not be given to a single value alone. In any case where there is significant doubt, serial spot methemoglobin should be obtained (as clinically indicated based on symptoms such as but not limited to skin discoloration, cyanosis, coma, or dysrhythmia and levels can be repeated every 6-8 hours until levels <20%) and consultation as needed.

It is expected that all patients will show a transient rise in methemoglobin (up to 10-15%) while on study but unless accompanied by hypoxia, or symptoms (e.g., dyspnea), no changes to treatment or dose may be required. However, for patients not fitting this pattern, the following guidelines should be followed:

- If methemoglobin is asymptomatic, <20%, and NOT accompanied by hypoxia (oxygen saturation <92%) : treat without change in dose.
- IF methemoglobin >15% lasts more than 3 hours OR if methemoglobin >20% OR if oxygen saturation <92%, THEN: obtain arterial blood gases (a pO2 <80 should result in hospitalization and will be counted as DLT). If pO2 normalizes within 24 hours, retreatment at a lower dose level may be considered by the Principal Investigator at UPCI.

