## 13. STATISTICAL CONSIDERATIONS

### 13.1 Study Design/Endpoints

The **primary safety endpoint** of this study is DLT, and the first primary objective is the determination of the MTD and recommended phase II dose for oral triapine when used concomitantly with cisplatin chemoradiation.

The **primary PK endpoint** of this study is oral bioavailability of triapine, which will be determined with sufficient precision that the 95% CI of the mean population bioavailability falls within 80-125% of that mean. Based on reported preliminary data and assuming a normal distribution at log base 10 level, a true bioavailability rate of 0.67, and a standard deviation of 0.175 at log base 10 level, with 28 patients on RP2D, we will be able to establish the bioavailability with the 95% confidence interval of the population mean falling within 0.53-0.83.

Other PK parameter, including AUC, Cmax, Tmax and T1/2 will be evaluated in the expansion cohort. Descriptive statistics will be used.

The **secondary efficacy endpoints** include metabolic complete response (mCR) by FDG-PET/CT, clinical overall response (OR), overall survival (OS) and progression free survival (PFS).

For the first dose level, 3 patients were enrolled without issues. Given the scarcity of patients and the thus far favorable toxicity profile, dose level 2 will be enrolled per an accelerated titration approach using a single patient cohort. Dose escalation will revert to the standard 3+3 design if the

patient on dose level 2 experiences a DLT or a  $\geq$  grade 2 toxicity or when dose level 3 is reached. The standard 3+3 design is as follows: Escalation at 0/3 DLTs, dose-reduction if  $>1/3$  DLT, and expansion to 6 if 1/3 DLTs. DLT is defined as the severe toxicity event that leads to the termination of the treatment as defined in section 5.5. The highest dose level where  $<2/6$  DLTs are observed will be declared MTD.

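### Section 13 makes a DLT count below 80% delivery only if it ended treatment, a condition Section 5.5 does not contain, so a patient with a true DLT can be replaced

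*Combined protocol and SAP*

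**What the plan says.** Section 5.5 lists the events that are DLTs if at least possibly related to study therapy and occurring before the end of external beam radiation. Stopping treatment is not a condition. The list includes "Any other non-hematologic toxicity" of Grade 3 or higher and two delivery criteria: "Inability to deliver at least 20 of the scheduled 25 administrations of triapine at the planned dose" (with two weeks allowed to make up missed radiation days) and "Inability to deliver at least 4 of the scheduled 5 administrations of IV cisplatin at the planned dose".

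Section 13 adds a condition in three places:

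- 13.1: "DLT is defined as the severe toxicity event that leads to the termination of the treatment as defined in section 5.5".
- 13.2.1, on who is not evaluable and is replaced: "Patients who do not complete at least 80% the first cycle of therapy and do not suffer a DLT which leads to the termination" of treatment during the observation period.
- 13.3.1: a patient is DLT-evaluable with at least 80% of the intended treatment, or if she received any amount and "experienced a protocol defined DLT which leads to the termination of the treatment are evaluable for DLT".

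Elsewhere the protocol describes DLTs that need not end treatment. In 6.6, a pO2 below 80 "should result in hospitalization and will be counted as DLT", yet if it normalizes within 24 hours "retreatment at a lower dose level may be considered by the Principal Investigator". In 6.5, Grade 3 non-hematologic toxicity leads to a hold with possible resumption, and only a delay of more than two weeks takes the patient off protocol therapy.

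**The concern.** DLT is the primary safety endpoint. In the expansion it drives the Bayesian suspension rule (13.1.1), and its rate at the RP2D is to be reported with an exact 95% confidence interval (13.3.3). The usual purpose of a minimum-exposure rule is to set aside patients who had too little treatment to show that a dose is tolerable. A patient who has already had a DLT has given her answer, whatever she received.

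Under 13.2.1 and 13.3.1 as written, a patient below 80% whose DLT did not end treatment is not evaluable and is replaced. Every such error acts in one direction: it removes a DLT and makes the regimen look safer.

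**Working it through.** **Step 1. Can such patients exist?** Under 13.3.1:

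| Patient | Received at least 80% | Received less than 80% |
|---|---|---|
| DLT that ended treatment | evaluable | evaluable |
| DLT, treatment continued | evaluable | **not evaluable, replaced** |
| No DLT | evaluable | not evaluable, replaced |

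Sections 6.5 and 6.6 show that the middle row is not empty. The delivery criteria in 5.5 sit exactly on the evaluability line: 20/25 = 80% and 4/5 = 80%. Counting doses given for each drug, a delivery-shortfall DLT therefore means at most 19/25 = 76% of triapine or 3/5 = 60% of cisplatin. On that basis such a patient is always below 80% and is kept only if treatment ended.

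**Step 2. How far does it reach?** The plan does not say how the 80% is measured. Three hypothetical patients who stay on treatment:

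| Delivery | Per drug, by count | Other bases |
|---|---|---|
| 25/25 triapine, 3/5 cisplatin | cisplatin 60%: out | pooled drugs 28/30 = 93%: in |
| 18/25 triapine, 5/5 cisplatin | triapine 72%: out | pooled drugs 23/30 = 77%: out; with 25 radiation fractions 48/55 = 87%: in |
| Triapine reduced from 100 to 50 mg from week 3, none missed | 25/25: in | at planned dose 10/25 = 40%: out; by mg (50 + 9×100 + 15×50)/(50 + 24×100) = 1700/2450 = 69%: out |

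The same patient can be in or out depending on an unstated choice.

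**Step 3. Reproduce the plan's figures.** With x DLTs in n patients, the posterior is Beta(1 + x, 5 + n − x), and accrual is suspended when P(rate > 20%) is at least 0.70. For example, 2 in 4 gives 0.738 (suspend) and 2 in 5 gives 0.678 (continue). All printed boundaries reproduce. Let P_n(k) be the probability of k DLTs after n patients without suspension. Then P_n(k) = (1 − p)·P_{n−1}(k) + p·P_{n−1}(k − 1), and probability at or above the boundary is removed at each n from 3 to 27.

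| True rate p | 0.10 | 0.17 | 0.20 | 0.25 | 0.30 |
|---|---|---|---|---|---|
| Printed (simulation) | 0.10 | 0.32 | 0.45 | 0.66 | 0.83 |
| Exact | 0.093 | 0.322 | 0.450 | 0.658 | 0.819 |

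**Step 4. Replace one DLT patient, if the rule uses the DLT-evaluable set.** Suppose the first patient with a DLT is replaced, so that neither n nor k advances and the next patient takes the place. Losing the first DLT is the worst single loss, because the count is then one lower at every later look.

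| True rate | All DLTs counted | First DLT patient replaced |
|---|---|---|
| 25% | 0.658 | 0.477 |
| 30% | 0.819 | 0.687 |

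Illustration only, because the documents give no share: if a fraction f of DLT patients is replaced, the rule sees p(1 − f)/(1 − pf). At p = 25%, f = 10% gives 0.225/0.975 = 23.1% and a suspension probability of 0.581. With f = 1/3 it sees 0.1667/0.9167 = 18.2%, and the probability is 0.372. With f = 0 it is 0.658.

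**Step 5. Reported rate.** If one of seven DLT patients among 28 is replaced by a patient without a DLT, the Clopper-Pearson result moves from 7/28 = 25.0% (10.7 to 44.9%) to 6/28 = 21.4% (8.3 to 41.0%).

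**The case against.** - **The termination phrase may only describe what DLTs usually do.** Grade 4 events under 6.1 to 6.5 do take the patient off protocol therapy, so those DLTs are counted either way. But the phrase then misdescribes 5.5 and 6.6, and anyone applying 13.2.1 literally would still replace the patient.
- **Many non-terminating DLTs leave the patient at or above 80%.** This stands. A brief interruption under 6.6 may cost few doses. The 18/25 case needs radiation to continue on all seven held days, although 6.5 holds radiation during Grade 3 toxicity and 5.2.1 and 5.5 allow make-up. With one day made up, the pooled figure is 24/30 = 80% and the patient is in. With two, triapine is 20/25 and there is no shortfall. So the route exists, but its frequency cannot be stated.
- **The DLT-evaluable set may not feed the decisions.** This also stands in part. The suspension table counts patients treated, 13.3.1 assigns safety analysis to the safety set, and 13.3.3 describes all DLTs patient by patient. Suspension is a pause for review, and toxicity is reviewed weekly. The plan does not name the set that supplies n and N or the reported rate, so steps 4 and 5 are conditional. A narrative listing would not put an omitted event back into either.
- **Losing the first DLT in every trial is severe.** Agreed. At a true rate of 25%, suspended trials contain about 3.5 DLTs on average, so one loss is a large share. It is an upper bound for a single loss, not an expected effect.

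A reader might go further and infer that the 100 mg MTD is biased, or that the escalation data already show an excluded DLT. The documents support neither. At 100 mg, six patients have PK data and six are evaluable, with one DLT. At 150 mg, four have PK data and three are evaluable, with two DLTs; adding the fourth still gives at least two. Ten treated and nine evaluable shows one non-evaluable patient, and the available text does not give the reason.

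**Conclusion.** The contradiction is certain on the text: three places in Section 13 impose a condition that 5.5 lacks and that 6.5 and 6.6 show need not be met. It is equally certain that a patient below 80% with a non-terminating DLT is, as written, replaced and not counted as evaluable.

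The size is not certain. It depends on how the 80% is measured, on make-up days, and on whether the DLT-evaluable set supplies the suspension rule and the reported rate. If it does, the step 4 and step 5 figures bound or illustrate the effect of one loss; if every DLT is counted, there is none.

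A reader might also infer that every non-terminating DLT is lost. That does not follow. Patients at or above 80% are evaluable under the first part of 13.3.1, and their DLTs drop out only if the phrase in 13.1 is taken to override its own reference to 5.5.

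**What to change.** Reconcile Section 13 with 5.5 and 6.6:

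1. Delete the termination condition in 13.1, 13.2.1 and 13.3.1.
2. Treat every treated patient with a protocol-defined DLT as DLT-evaluable, whatever the amount delivered and whether or not treatment stopped.
3. Apply the 80% requirement, and replacement, only to patients without a DLT.
4. State one basis for the 80%, consistent with the delivery limits in 5.5, and say whether the sixth cisplatin cycle permitted in 5.3.1 counts toward it.
5. Name this set as the source of n and N in the suspension table and of the reported DLT rate and its interval.
6. Re-check the patients treated so far against the reconciled definition.

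No dosing, hold or stopping rule changes. The cost is a few sentences and the re-check. The observed DLT rate may become slightly less favourable.

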### 6.3 Neutropenia

Neutropenia	Management/Next Dose for Triapine	Management/Next Dose for Cisplatin
≤ Grade 2	No change in dose	No change in dose
Grade 3	No change in dose	Hold a week-to-week until ≤ Grade 2. Resume at same dose level
Grade 4	Off protocol therapy b	Off protocol therapy b

aPatients requiring a delay of >2 weeks should go off protocol therapy.

bOff protocol therapy and continue standard of care treatment per treating physician.

- G-CSF is not allowed during this therapy
- External-beam pelvic radiation and Triapine dosing should continue while any or all courses of cisplatin are withheld.

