### 6.5 Non-hematologic toxicity

Non-hematologic toxicity	Management/Next Dose for Triapine	Management/Next Dose for Cisplatin
≤ Grade 1	No change in dose	No change in dose
Grade 2	Hold a until ≤ Grade 1 (SEE NOTE)	Hold a until ≤ Grade 1. (SEE NOTE)
Grade 3	Hold a until < Grade 1 (SEE NOTE)	Hold a until < Grade 2. (SEE NOTE)
Grade 4	Off protocol therapy b	Off protocol therapy b

aPatients requiring a delay of >2 weeks should go off protocol therapy.

bOff protocol therapy and continue standard of care treatment per treating physician.

cNOTE: Decision to maintain dose or resume at dose reduction must be reviewed with study PI

- External-beam pelvic radiation should be held until Grade 3 toxicity is ≤Grade 2.

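### Sections 13.2.1 and 13.3.1 drop and replace a patient below 80% of treatment whose DLT did not end treatment, although 5.5 sets no such condition and section 6 lets dosing go on after some DLTs

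*Combined protocol and SAP*

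**What the plan says.** **Statistical section.** Three places attach the end of treatment to a DLT.

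- 13.1: "DLT is defined as the severe toxicity event that leads to the termination of the treatment as defined in section 5.5".
- 13.2.1: patients below 80% of the first cycle who "do not suffer a DLT which leads to the termination of the treatment during the observation period" are not evaluable and are replaced.
- 13.3.1: a patient is evaluable for DLT if she received at least 80% of the treatment intended in the DLT period. A patient with any lesser amount is evaluable if she "experienced a protocol defined DLT which leads to the termination of the treatment are evaluable for DLT".

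**Clinical sections.** Section 5.5 lists the DLT events and requires only that they be at least possibly related and fall within the EBRT period. The list includes most Grade 3 non-hematologic toxicities and "Inability to deliver at least 4 of the scheduled 5 administrations of IV cisplatin at the planned dose". Section 6 then allows treatment to go on after some of these events.

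- 6.5: after Grade 3 non-hematologic toxicity, dosing is held. Then: "Decision to maintain dose or resume at dose reduction must be reviewed with study PI". Only Grade 4 or a delay of more than 2 weeks ends protocol therapy.
- 6.6: an arterial pO2 below 80 "should result in hospitalization and will be counted as DLT". If it normalizes within 24 hours, "retreatment at a lower dose level may be considered by the Principal Investigator".
- 6.3, with the same rule in 6.4: radiation and "Triapine dosing should continue while any or all courses of cisplatin are withheld".

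**The concern.** DLT is the primary safety endpoint. It feeds the Bayesian suspension rule in 13.1.1 and the DLT rate at the RP2D, with exact 95% CI, in 13.3.3. A patient whose DLT causes held or reduced doses, and who therefore ends below 80%, is someone the safety assessment most needs to keep. Under 13.2.1 and 13.3.1 as written, she is kept only if treatment was also stopped. If she carried on, she is removed and someone else takes her place. The error runs one way: every patient lost by this route has had a DLT, so the observed rate can only fall.

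**Working it through.** **1. Which DLTs can occur without treatment ending**

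| Event | DLT under | Can treatment go on? | Can she fall below 80%? |
|---|---|---|---|
| Grade 3 non-hematologic toxicity (other than nausea, vomiting, diarrhea, creatinine) | 5.5 | Yes, after a hold and PI review (6.5) | Yes, if held doses are not made up |
| pO2 below 80 | 6.6 | Yes, at a lower dose, if normal within 24 hours | Possible |
| Fewer than 4 of 5 cisplatin doses | 5.5 | Yes; radiation and triapine continue (6.3, 6.4) | Depends on how 80% is measured |
| Grade 4 events taken off protocol therapy by 6.1 to 6.5 | 5.5 | No | Not affected |

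For the cisplatin case, two held courses leave 5 − 2 = 3 of 5 unless the sixth-week dose allowed in 5.3.1 makes one up. Judged per agent, 3/5 = 60%, which is below 80%. Judged over both drugs with triapine complete, (3 + 25)/(5 + 25) = 28/30 = 93%, and she stays evaluable. The plan does not say which measure applies.

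**2. The plan's own figures reproduce**

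Inputs from 13.1.1: prior Beta(1, 5); suspend when P(DLT rate > 0.20) is at least 0.70; boundaries 2 in 3–4, 3 in 5–8, 4 in 9–13, 5 in 14–17, 6 in 18–22, 7 in 23–26 and 8 in 27; at most 28 patients. The posterior after x DLTs in n patients is Beta(1 + x, 5 + n − x). An exact binomial recursion over the published boundaries gives:

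| True DLT rate | Plan | Recomputed |
|---|---|---|
| 0.10 | 0.10 | 0.093 |
| 0.17 | 0.32 | 0.322 |
| 0.20 | 0.45 | 0.450 |
| 0.25 | 0.66 | 0.658 |
| 0.30 | 0.83 | 0.819 |

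**3. Effect of replacement**

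Let p be the true DLT rate and f the share of DLTs in patients who continue treatment. If all of these patients are replaced, the rate the rule sees is p(1 − f)/(1 − pf). The documents give no value for f, so 10%, 20% and 30% are assumptions.

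| p | f | Rate seen by the rule | Suspension probability |
|---|---|---|---|
| 0.30 | 0 | 0.300 | 0.819 |
| 0.30 | 10% | 0.270/0.970 = 0.278 | 0.757 |
| 0.30 | 20% | 0.240/0.940 = 0.255 | 0.678 |
| 0.30 | 30% | 0.210/0.910 = 0.231 | 0.581 |
| 0.25 | 0 | 0.250 | 0.658 |
| 0.25 | 10% | 0.225/0.975 = 0.231 | 0.581 |
| 0.25 | 20% | 0.200/0.950 = 0.211 | 0.496 |
| 0.25 | 30% | 0.175/0.925 = 0.189 | 0.403 |

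For a given f these falls are upper bounds, because they put every continuing DLT patient below 80%.

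**4. One patient at the boundary**

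Four DLTs in 13 give Beta(5, 14) and a posterior of 0.716, so accrual is suspended. If one of those four is dropped, 3 in 12 gives Beta(4, 14) and 0.549, and accrual continues.

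**The case against.** **5.5 may be meant to govern.** The sentence in 13.1 refers to 5.5, and 5.1.2, the 13.1.1 table and 13.3.3 use DLT without a termination condition. This stands for counting. A reader might infer from 13.1 that a patient who completes 80% or more and continues after a DLT goes uncounted. The documents do not support that with any firmness: the cross-reference points the other way, and 6.6 says outright that its event counts. No size is therefore attached to that reading. The argument does not rescue 13.3.1, which starts from a protocol-defined DLT and then adds termination, or 13.2.1, which directs replacement.

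**The route to replacement is narrow.** It takes a DLT, continued treatment and less than 80% delivered. Two make-up weeks are allowed. Section 13.2.1 measures 80% of the first cycle, and 5.3.1 calls each cisplatin week a cycle, so on that usage a patient who completes week 1 could not be replaced under 13.2.1. The same sentence refers to a 5-week observation period, which leaves the matter unclear. Section 13.3.1 applies its 80% to the DLT follow-up period in either case. This objection stands as a limit on size.

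**Section 5.5 does not itself let patients continue.** Correct. It only sets no termination condition; the permission comes from 6.3 to 6.6.

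**Safeguards exist.** Suspension leads to a review, not automatic termination. DLTs are reviewed weekly, and all DLTs and Grade 3 or higher events are described patient by patient. These help, but they do not put a replaced patient back into the suspension count or the DLT-evaluable set.

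**The escalation result.** A reader might infer that the 1 of 6 at 100 mg is understated. Nothing available shows this: the descriptions of the individual DLTs are not in the reviewed text.

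**Conclusion.** The point holds as a conflict between the evaluability and replacement rules and the DLT definition. As written, a patient with a 5.5 or 6.6 DLT who continues and falls below 80% is dropped and replaced. The cisplatin-delivery DLT is caught only if the 80% is judged per agent. The direction of the bias is certain; its size is not known. At assumed shares of 10% to 30%, the upper-bound loss in suspension probability is 0.06 to 0.24 at a true rate of 30% (0.819 − 0.757 and 0.819 − 0.581), and 0.08 to 0.25 at a true 25% (0.658 − 0.581 and 0.658 − 0.403). The real loss may be much smaller. Because the endpoint is primary and the repair is a few words, the text should be corrected. No past DLT count and no MTD decision is put in doubt.

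**What to change.** Delete the condition that the DLT led to the end of treatment from 13.2.1 and 13.3.1, and the matching phrase from 13.1. State that any DLT under 5.5 or 6.6 counts, makes the patient evaluable and bars her replacement, whether or not treatment continues. Adding the pO2 criterion of 6.6 to the 5.5 list would be tidy but is editorial, since 6.6 already makes it a DLT.

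The cost is a wording amendment, with a somewhat higher observed DLT rate and a higher chance of a suspension review. The rise cannot be sized from the documents. One item to settle at the same time is Grade 4 lymphocyte decrease. It falls under the Grade 4 hematologic criterion of 5.5, has no stopping rule in section 6, and was the worst grade in 3 of 10 patients in the escalation adverse event table. If it is not meant to count, 5.5 is the place to say so.
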